9.30. Questionnaire of Smoking Urges – Brief (QSU-Brief)

The Brief Questionnaire of Smoking Urges (QSU-Brief) consists of ten statements regarding the respondent's desire to smoke cigarettes at the time of assessment (i.e. now). This ten item questionnaire measures agreement or disagreement with each statement by means of a 7-point scale where '1' indicates "strongly disagree" and '7' indicates "strongly agree." This assessment takes less than two minutes to administer and will be utilized at screening and all follow-up visits.

9.31. Readiness to Change (RTC) Ladder (cigarette use/alcohol use)

The Readiness to Change Ladder is a measure with 11 response items designed to assess motivation to reduce or cut back on smoking and drinking. This assessment will be completed at the initial screening visit.

9.32. Saliva Collection

Normally-cycling and hormonal contraceptive using women will provide saliva samples for hormonal testing at medication titration and on each return to the laboratory for follow-ups 4, 8, 12, 16 and 26 weeks post quit date. Self-reported menstrual cycle phase will be confirmed by measuring levels of estradiol (E2) and progesterone (P4).

9.33. Self-Reported Habit Index Form (cigarette use/alcohol use)

The Self-Reported Habit Index Form is a 12-item index of habit strength for cigarette and alcohol use that will be completed at the initial screening visit. Responses will be self-reported by participants directly into the electronic data capture system.

9.34. Smoking History Questionnaire (SHQ)

The Smoking History Questionnaire will collect information on frequency and quantity of nicotine use. Participants will directly enter responses into the EDC system at the initial screening visit.

9.35. Structured Clinical Interview (SCID)

The SCID is a semi-structured interview for making the major DSM Axis-I diagnoses. It will be assessed by appropriately trained research staff to all participants at the initial screening visit to determine alcohol use disorder and rule out other exclusionary diagnoses.

9.36. 30-day Timeline Followback (TLFB)

The Time Line Follow Back will be administered for both alcohol use and cigarette smoking at initial screening, medication titration, and at all follow up visits. Information obtained in this interview will be recorded on the TLFB Calendar and transcribed to the database.

9.37. Urine Cotinine Levels

Participants will be asked to provide a urine specimen at the initial screening visit for testing of cotinine levels to verify that the participant is a regular smoker and at all follow up visits to assess for smoking abstinence.

9.38. Urine Drug Screen

An FDA cleared, CLIA waived urine drug test card will be used at the initial screening, medical screening and medication titration visits to assess candidates for recent use of opioids, cocaine, amphetamines, methamphetamine, THC, buprenorphine, methadone or benzodiazepines. Subjects must be negative for all substances except THC. Results will be recorded on the visit checklist first and then entered into the database.

9.39. Vital Signs

Vital signs assessed at each visit include sitting blood pressure and pulse rate (after sitting for at least 3 minutes) and weight. Values will be recorded on the visit checklist and entered into the database.

9.40. Wisconsin Inventory of Smoking Dependence Motives (WISDM)

The Wisconsin Inventory of Smoking Dependence Motives (WISDM-68) assesses 13 varied smoking motives in order to assess processes that may lead to nicotine dependence. Responses to this measure will be directly entered by the participant at the initial screening visit.

9.41. Wisconsin Predicting Patient's Relapse (WI-PREPARE)

The Wisconsin Predicting Patient's Relapse is a brief, seven-item questionnaire that taps physical dependence, environmental factors, and individual difference characteristics to suggest the nature of a patient's short- and medium-term relapse risk. The WI-PREPARE will be assessed at the initial screening visit with direct data entry by the participant.

9.42. Yale Craving Scale (YCS)

The Yale Craving Scale will be used to assess smoking and drinking urges at initial screening. This measure utilizes a generalized Labeled Magnitude Scale, which will be assessed by participants on paper and later scored and entered into the database.

10. ETHICS

10.1. IRB Review

The study will be conducted under a protocol reviewed by the UCLA IRB; the study is to be conducted by scientifically and medically qualified persons; the benefits of the study are in proportion to the risks; the rights and welfare of the subjects will be respected; the physicians conducting the study will ensure that the hazards do not outweigh the potential benefits; the results to be reported will be accurate; subjects will give their informed consent and will be competent to do so and not under duress; and all study staff will comply with the ethical principles in 21 Code of Federal Regulations (CFR) Part 50 and the Belmont Principles.

10.1.1. Protocol Modifications

All necessary protocol changes will be submitted in writing as protocol amendments to the IRB by the PI for approval prior to implementation.

10.1.2. Protocol Deviation Reporting Procedures

All subject-specific deviations from the protocol are to be documented. The PI or designee will be responsible for identifying and reporting all deviations, which are occurrences involving a procedure that did not follow the study protocol. Any protocol deviation that adversely affects the safety or rights of a subject or scientific integrity of the study is considered a major deviation and will be reported immediately to the UCLA IRB.

10.2. Ethical Conduct of the Study

This study will be conducted in accordance with all applicable Federal human research protections requirements and the Belmont Principles of respect for persons, beneficence, and justice.

The procedures set out in this study are designed to ensure that all study personnel abide by the principles of the ICH GCP Guideline and the Code of Federal Regulations (CFR). The PI confirms this by signing FDA Form 1572.

10.2.1. Confidentiality of Data and Subject Records

To maintain subject confidentiality, all laboratory specimens, eCRFs, reports and other records will be identified by a subject number only. Research and clinical records will be stored in a locked cabinet. Only research staff, sponsor officials, and other required regulatory representatives will have access to the records. Subject information will not be released without written permission. The PI has received a Certificate of Confidentiality for this study.

10.2.2. Compensation for Participation

Subjects will be compensated for travel expenses and for time contributed to this research study in the form of cash. Compensation will be provided at each subject visit and is detailed in the informed consent form.

10.2.3. Written Informed Consent

The informed consent process and document will be reviewed and approved by the IRB and prior to initiation of the study. The consent document contains a full explanation of the possible risks, advantages, and alternate treatment options, and availability of treatment in the case of injury, in accordance with 21 CFR Part 50. The consent document indicates that by signature, the subject, permits access to relevant medical records as described above. A written informed consent document, in compliance with 21 CFR Part 50, 32 CFR Part 219, and the Belmont Principles, and HIPAA Authorization will be signed by the subject before any study-related procedures are initiated for each subject. All potential subjects for the study will be given a current copy of the Informed Consent Form to read. All aspects of the study and informed consent will be explained in lay language to the subject by either the investigator, or a medically trained designee. Any subject who is unable to demonstrate understanding of the information contained in the informed consent will be excluded from study participation. All study subjects will be given a copy of the signed informed consent.

10.2.4. Delegation of Responsibilities and Adequate Resources

The PI should have adequate time to conduct the study properly and should have an adequate number of qualified staff to assist with the conduct of the study. The term “investigator” used throughout this protocol refers to the PI and/or qualified Sub-investigators. The PI may delegate responsibilities to other study site personnel. The PI shall delegate tasks only to individuals qualified by education, training, and experience to perform the delegated tasks. The PI shall have direct oversight of all delegated activities and shall document delegation of responsibilities. The PI is responsible for ensuring all delegated staff has been properly trained on the protocol and their assigned study responsibilities. A delegation log identifying all delegated duties and the individual to whom they have been delegated will be maintained at the study site.

10.2.5. Financial Disclosure

Clinical investigators are required to provide financial disclosure information for the submission of certification or disclosure statements required under 21 CFR § 54. As defined in 21 CFR §54.2, a clinical investigator is a listed or identified investigator or sub-investigator who is directly involved in the treatment or evaluation of research subjects. The term also includes the spouse and each dependent child of the investigator. In addition, investigators must promptly update financial disclosure information if any relevant changes occur during the course of the investigation and for 1 year following completion of the study.

11. DATA HANDLING AND RECORD KEEPING

Source documents include but are not limited to original documents, data and records such as hospital/medical records (including electronic health records), clinic charts, laboratory results, data recorded in automated instruments, and pharmacy records, etc. This study will use an electronic data capture (EDC) eCRF system (MediaLab) and paper source documents. Data will be transcribed from source documentation directly into a statistical program such as SPSS. Only questionnaire data will be entered directly into eCRF (i.e., without prior written or electronic record of data). Paper copies of the eCRFs will be available in the event that the EDC is not accessible at the time the questionnaire is being completed. The transcribed data will be consistent with the source documents or the discrepancies will be explained. All entries, corrections, and alterations will be made by the investigator or other authorized study personnel. The EDC system maintains a full audit trail of data entry, data corrections, and data queries.

11.1. Subject Identification and Confidentiality

Subjects will be identified on eCRFs and paper source documents by a unique subject number. No personal identifier will be used in any publication or communication used to support this research study. The subject number will be used if it becomes necessary to identify data specific to a single subject. Regulatory bodies, such as the study sponsor, National Institute of Drug Abuse (NIDA), FDA, IRB, and the FDA are eligible to review medical and research records related to this study as a part of their responsibility to protect human subjects in clinical research. Personal identifiers will be removed from photocopied or electronic medical and research records.

11.2. Retention of Records

The investigator is responsible for creating and/or maintaining all study documentation required by Title 21 Code of Federal Regulations (21CFR) Parts 50, 54, 56, and 312, ICH E6 section 8, as well as any other documentation defined in the protocol. The investigator must provide key documents to the Sponsor prior to start of the study. Federal and local regulations require that the investigator retain a copy of all regulatory documents and records that support the data for this study for whichever of the following is the longest period of time:

- A period of 2 years following the final date of approval by the FDA or other regulatory agency of the study drug for the purposes that were the subject of the investigation; or
- A period of 5 years following the date on which the results of the investigation were submitted to the FDA or other regulatory agency in support of, or as part of, an application for a research or marketing permit for the study drug for the purposes that were the subject of the investigation.

If the investigator retires, relocates, or for other reasons withdraws from the responsibility of keeping the study records, custody must be transferred to a person who will accept the responsibility. The Sponsor must be notified in writing of the name and

address of the new custodian. Study records should not be destroyed without consultation with the Sponsor.

11.3. Trial Registration

The PI will register the trial on the National Library of Medicine's Clinical Trials Registry at <http://www.clinicaltrials.gov>.

13. APPENDICES

- 13.1. Appendix 1: Schema of Study Procedures**
- 13.2. Appendix 2: Schedule of Assessments**
- 13.3. Appendix 3: Medication Information Sheets**
- 13.4. Appendix 4: Smoking Cessation Counseling Manual**

Combining Varenicline and Naltrexone for Smoking Cessation and Drinking Reduction

DATA ANALYSIS PLAN

NCT02698215

October 2018

Analyses were conducted in SAS Statistical Software Version 9.4. All analyses were of the intention-to-treat type. Since all participants took the first dose of the study medication under observation during the randomization visit, all participants were included in the subsequent analyses. The dichotomous primary outcome for smoking cessation at the 26-week follow up was analyzed using a Chi-Square test comparing smoking cessation rates for the two medication conditions. For the purpose of these analyses, all individuals who dropped out from the trial were considered to have returned to smoking, per guidelines for smoking cessation trials. For the drinking outcomes, all of which were continuous, a series of multilevel models, via Proc Mixed, were conducted for each outcome separately, during the 12-week treatment period and for the entire 26-weeks of the trial, which is consistent with pharmacotherapy trials for excessive drinking. These models tested whether the two medication groups differed in alcohol use over the 12-week medication period and across the entire 26-weeks of the trial. All models for drinking outcomes controlled for baseline drinking levels.

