denicotinized cigarettes [31, 32]. Alcohol also offsets some of the effects of the nicotine antagonist mecamylamine, which reduces satisfaction with smoking [32]. Of clinical importance, greater alcohol use is associated with decreased odds of smoking cessation [7, 8] and it is estimated that smokers are 4 times more likely to experience a smoking lapse during drinking episodes. A recent study of tobacco quitline callers found that hazardous drinkers had lower smoking cessation rates compared to moderate drinkers [4]. Given the co-occurrence of smoking and drinking and the neurobiological interactions between alcohol and nicotine, it has been convincingly argued that heavy drinking smokers constitute a distinct sub-population of smokers with a unique clinical profile and treatment needs [2, 9]. Although practice guidelines recommend smokers be advised to reduce or avoid drinking alcohol when making a quit attempt [19], there are no available pharmacological treatments or guidelines tailored to heavy drinking smokers, a sizeable and treatment-resistant sub-group. And while a recent behavioral treatment study found some support for incorporating a brief alcohol intervention to improve smoking cessation among heavy drinking smokers [33], no pharmacological studies to date have combined medications for smoking and drinking for this population. Thus, treatment development for heavy drinking smokers represents a highly significant and understudied research area.

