2.2. Varenicline: effective for smoking cessation and may reduce alcohol use

A number of pharmacological treatments have been developed for nicotine dependence. Nicotine replacement therapy appears to be modestly effective, presumably by decreasing withdrawal [34]. Bupropion is another medication with moderate effectiveness, although its mechanisms of action remain relatively unclear. It is thought that the effect of bupropion on dopamine, noradrenaline, or even its direct effects on nicotine receptors may be involved in its clinical efficacy [35]. More recently, varenicline has been approved for the treatment of tobacco dependence. Molecular studies have convincingly demonstrated that the $\alpha 4\beta 2$ subtype is necessary for nicotine dependence [36, 37]. Developed to address the critical role of $\alpha 4\beta 2$ in tobacco dependence, varenicline is a partial agonist at $\alpha 4\beta 2$ receptors. The putative mechanisms of action of varenicline stem from the stimulation of dopamine release (as a partial nicotine agonist) [38] and with its ability to block the binding of nicotine to its site (an antagonist effect), which in turn results in reductions in nicotine craving and reward [39]. At the behavioral level, varenicline-induced blockade of $\alpha 4\beta 2$ nAChRs reduces craving and withdrawal and attenuates the rewarding effects of smoking [39-43]. Functional neuroimaging studies found that varenicline increases activation of the dorsal anterior cingulate/medial frontal cortex, and dorsolateral prefrontal cortex during a working memory task [44] as well as during an emotional processing task [45]. Moreover, varenicline diminished smoking cue-elicited ventral striatum and medial orbitofrontal cortex responses compared to placebo [46]. Perhaps most importantly, a number of clinical trials found that varenicline is more effective than bupropion [10], superior to nicotine replacement therapy [47], and significantly more effective than placebo [10, 48-51] as a smoking cessation agent. As a result of this compelling clinical data, varenicline was advanced as a first line treatment for nicotine dependence [52]. It is to be noted, however, that abstinence rates on varenicline are about 43% at 12

weeks and 25% at one-year follow-up [53]. Thus, even though varenicline is superior to other treatments, there is a clear opportunity to improve upon these clinical outcomes, particularly among hard-to-treat sub-groups such as heavy drinking smokers.

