7.4. Medication Titration/Stabilization Period

7.4.1. Randomization and Medication Titration Visit

Participants who are eligible after the medical screening visit will be scheduled to come into the lab to be randomized and start study medication. Subjects will be urn randomized to one of two medication groups. Urn randomization will be used to balance the two medication groups by gender, number of cigarettes per day, and drinks per drinking day. At this visit, a quit date will be set for day 14 of the medication titration/stabilization regimen.

Female participants will be asked about their menstrual cycle and reproductive status and will answer questions about hormonal responses and symptoms (see Schedule of Assessments). In addition, female participants of child-bearing potential will provide a saliva sample for testing of progesterone and estradiol levels and urine will be tested for surges in luteinizing hormone (LH).

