9.10. Demographics

Demographics data include the participant's age, gender, race/ethnicity, marital status, education, employment pattern, occupation, and income level. These data will be collected by site staff at the initial screening visit on a source document and entered into an eCRF.

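### The week-26 smoking test is a valid chi-square that uses none of the three urn-randomisation factors; adjusting for them might gain a little power, about 2 points at most under the strengths assumed here

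*SAP*

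**What the plan says.** The SAP, a single-page plan dated October 2018, states that the dichotomous week-26 cessation outcome "was analyzed using a Chi-Square test comparing smoking cessation rates for the two medication conditions". Participants who drop out count as smoking, so everyone randomised enters the test. No covariate or stratification factor is named for it.

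Protocol 7.4.1 states: "Urn randomization will be used to balance the two medication groups by gender, number of cigarettes per day, and drinks per drinking day". Section 4 sets the sample at 274, 137 per arm.

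The SAP adjusts elsewhere: "All models for drinking outcomes controlled for baseline drinking levels".

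All three urn factors are measured before treatment:
- Gender is among the demographics in Protocol 9.10: "age, gender, race/ethnicity, marital status, education, employment pattern, occupation, and income level".
- For cigarettes per day, Protocol 9.34 says: "The Smoking History Questionnaire will collect information on frequency and quantity of nicotine use".
- Drinking and smoking counts also come from Protocol 9.36: "The Time Line Follow Back will be administered for both alcohol use and cigarette smoking at initial screening", and again at the titration visit.

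Protocol 2.1 links one factor to the outcome: "greater alcohol use is associated with decreased odds of smoking cessation".

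Protocol 3.3 (aim s1b) asks whether abstinence differs between men and women, overall and by medication condition. It gives no model and does not adjust the week-26 treatment comparison.

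**The concern.** Balancing the arms on a factor that predicts the outcome makes the treatment estimate less variable across possible allocations. A test that ignores the factor does not credit that gain: its standard error is a little too large, so it rejects slightly less often than its nominal level. A model containing the factors recovers the difference and may also explain some outcome variation.

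The trial already collects these factors and runs the urn on them, so using them in the analysis needs no new data. The possible loss is some power on the main smoking comparison. Its size depends on how strongly the factors predict week-26 cessation, which neither document states.

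**Working it through.** **Inputs from the documents.** 274 participants, 1:1; two-group chi-square at week 26; dropouts counted as smoking; three urn factors. The documents state no alpha, power, effect size or planning rate for the 274, so that figure cannot be reproduced. Protocol 2.2 gives background rates only: "abstinence rates on varenicline are about 43% at 12" weeks, and 25% at one year. Neither is a week-26 rate in heavy drinkers.

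**Assumptions.** Two-sided 0.05; treated-arm rates of 41% (against 25%) and 60% (against 43%), chosen to give about 80% power; odds ratios (OR) per standard deviation (SD) of 1, 1.22 or 1.49; a marginal urn with median splits of cigarettes per day and drinks per drinking day (DPDD).

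**Starting point.** Chi-square power with n = 137 per arm:

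Φ{ [ |p₁ − p₀|·√n − 1.96·√(2p̄(1 − p̄)) ] / √(p₀(1 − p₀) + p₁(1 − p₁)) }

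- 25% vs 41%: (0.16 × 11.705 − 1.96 × 0.665) / 0.655 = 0.869, so power is 0.808.
- 43% vs 60%: (0.17 × 11.705 − 1.96 × 0.707) / 0.696 = 0.868, so power is 0.807.

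**Simulation.** There were 20,000 trials per scenario under the alternative and 20,000 under the null. The adjusted test is the Wald test of treatment in a logistic model with the three factors. The size-matched column compares the two tests with each held at exactly 5% rejection under the null (SE about 0.2 point).

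| Rates | Prognostic factors | Power, chi-square / adjusted | Raw gain (points) | Null rejection, chi-square / adjusted | Size-matched gain (points) |
|---|---|---|---|---|---|
| 25 vs 41% | none | 80.2 / 79.9% | -0.3 | 5.0 / 5.1% | -0.5 |
| 25 vs 41% | DPDD only, OR 1.22 | 81.2 / 81.3% | +0.1 | 4.9 / 5.0% | 0.0 |
| 25 vs 41% | DPDD only, OR 1.49 | 80.6 / 81.4% | +0.8 | 4.8 / 5.1% | +0.1 |
| 25 vs 41% | all three, OR 1.22 | 81.3 / 82.0% | +0.7 | 4.8 / 4.8% | +0.7 |
| 25 vs 41% | all three, OR 1.49 | 81.5 / 84.3% | +2.8 | 4.5 / 4.8% | +2.0 |
| 43 vs 60% | none | 80.3 / 80.7% | +0.4 | 4.7 / 4.7% | -0.4 |
| 43 vs 60% | DPDD only, OR 1.49 | 80.8 / 82.5% | +1.7 | 4.7 / 5.0% | +1.2 |
| 43 vs 60% | all three, OR 1.22 | 80.7 / 82.2% | +1.5 | 4.7 / 4.9% | +1.0 |
| 43 vs 60% | all three, OR 1.49 | 80.9 / 84.8% | +3.8 | 4.4 / 4.9% | +1.8 |

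The Monte Carlo SE of a null rate is 0.15 point. The chi-square's null rate never exceeds 5.0%.

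**Effective sample size.** Using 1/(SD ratio)², where the ratio is the SD of the adjusted risk difference over that of the unadjusted one:
- All three at OR 1.49, 43% vs 60%: 1/0.972² = 1.058, about +16 of 274.
- No prognostic factor: 1/1.004² = 0.992, about -2 of 274.
- DPDD only, OR 1.49: 1/0.994² = 1.012 (25% vs 41%) and 1/0.990² = 1.020 (43% vs 60%).

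**Second check.** A separate simulation used three binary factors, 8,000 runs per setting, 25% vs 41.4%. For ORs of 1, 1.5, 2 and 3 on every factor, raw gains were -0.1, +0.7, +1.9 and +4.7 points. Chi-square null rejection was 5.0, 4.6, 4.6 and 4.5%; the adjusted test's was 4.9, 4.8, 4.9 and 5.3%. An evenly split binary factor has SD 0.5, so OR 3 is √3 = 1.73 per SD, beyond the range in the table. The +4.7 is not size-matched, so part of it reflects the different null rates.

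**The case against.** The strongest reply is that nothing here is wrong. The SAP names one valid test of a binary endpoint, and preferring an adjusted model is a matter of efficiency. That stands, and the point is limited accordingly.

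Other parts of the reply also stand:
- A reader might take the raw gains of about 3 to 4 points as the benefit. The documents do not support that. It needs all three factors to be fairly strong, and part of it is the chi-square's conservatism. At equal size the largest gains are +2.0 and +1.8.
- In the case closest to the documents, only drinking matters. At 25% vs 41% the size-matched gain cannot be told from zero. The +1.2 arises at 43% vs 60%, where 43% is a 12-week rate.
- Everyone enrolled is a heavy drinker, so the association in Protocol 2.1 may be weaker within this sample.
- In the simulations the two tests fell on opposite sides of 0.05 in about 2% to 6% of trials. A reader might infer that the result is ambiguous. It is not, because the SAP names only one test. The figure matters only if a second test is added, and is then a reason to say which one decides.
- The contrast with the drinking models is not like for like. They adjust for the baseline of their own outcome, whereas everyone smokes at baseline. It is not an inconsistency in the SAP.

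Aim s1b does not answer the point. It is a question about sex differences with no stated model, and leaves the week-26 test as it is.

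**Conclusion.** The point holds as a small, optional improvement. The week-26 chi-square uses none of the three urn factors, and the documents give no other adjusted analysis of the smoking treatment effect. The test is valid: a reader might infer that leaving out balancing factors inflates type I error, but in the scenarios run it rejected 4.4% to 5.0% of the time under the null.

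At equal size, adjustment is worth about -0.5 to +2 points of power for odds ratios up to 1.49 per SD, and about 0 to +1 point if only drinking is prognostic. Stronger factors would give more. The covariate strengths, treated-arm rates, urn scheme and cut-points are all assumptions.

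**What to change.** **If set before outcome data are seen.** Analyse week-26 cessation, dropouts counted as smoking, with a logistic model of treatment, gender, baseline cigarettes per day and baseline drinks per drinking day. Take the pre-randomisation values used for the urn, and name their source and visit: cigarettes per day could come from the Smoking History Questionnaire or the Timeline Followback, and the latter is taken at both screening and titration. Enter the two counts as continuous. Make the treatment test in this model the single deciding test at two-sided 0.05. Report a standardised risk difference with 95% CI, and keep the chi-square as a sensitivity analysis that does not decide.

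**If outcomes had already been seen.** Keep the chi-square as the only deciding test and report the adjusted model as post hoc and supportive. The SAP's date and its past tense suggest that this may be the only version still open.

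**Cost.** SAP wording and a few lines of code; no new data. If no factor is prognostic, adjustment can lose up to about 0.5 point of power. Simulated coverage of a delta-method 95% CI for the standardised risk difference was 94.2% to 95.0%, so it may be very slightly short. No change to the drinking models is proposed.
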